This Clinical Investigational Plan (CIP), informed consent forms (ICF), recruitment materials, and all participant materials will be submitted to the Institutional Review Board (IRB) for review and approval. Approval of the CIP and the ICF must be obtained before any subject is enrolled. Any amendment to the CIP will require review and approval by the IRB before the changes are implemented to the study. In addition, all changes to the ICF will be IRB-approved and a determination will be made regarding whether a new consent needs to be obtained from subjects who previously provided consent.

INVESTIGATOR SIGNATURE PAGE

Investigator Name

Title

Site Name

Site Number

Date

I have read the protocol and agree that it contains all necessary details for carrying out this study. I will conduct the study as outlined therein.

I agree to keep records on all subject information (e.g., source documents and informed consent forms), device shipments and return forms, and all other information collected during the study, in accordance with local and national regulations.

Investigator Signature

SYNOPSIS

Study Title	Latera RCT – Latera [®] Absorbable Nasal Implant vs. Sham Control for Lateral Nasal Valve Collapse		
Spirox Protocol Number	CP04		
Investigational Device	Spirox Latera Absorbable Nasal Implant		
ClinicalTrials.gov Identifier	NCT 03400787		
Sponsor	Spirox, Inc. [name]		
Study Purpose	To evaluate the Latera Absorbable Nasal Implant (Latera Implant) Implant versus Sham Control in subjects with nasal valve collapse due to or primarily due to insufficient cartilaginous support of the lateral nasal wall		
Objective	The primary objective of the LATERA RCT is to demonstrate the superiority of the Latera Implant to improve nasal breathing, compared with a Sham Control treatment.		
Phase of Study	Post-market		
Study Design	Randomized (1:1), sham-controlled, single-blind, multicenter pos market trial using an adaptive trial design		
Investigational Sites	Up to 15 investigational sites in the United States, in office-based locations with investigators experienced in standard nasal interventions for airway obstructions and the use of the Latera Implant		
Study Population	The Adaptive Design allows for enrollment of up to 150 subjects with nasal airway obstruction due to or primarily due to nasal valve collapse.		

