#### 2.4 Sample Size Considerations

The primary analysis will be based on a 1-sided binomial test of proportions. Assuming a Sham Control response rate of 40% and a Latera Treatment response rate of 70% at month 3, a maximum sample size of 124 evaluable subjects is required for 90% power and preserving a 2.5% (one-sided) type I error rate. This study is designed as a group-sequential trial with 2 interim analyses and a final analysis. The stopping boundaries are derived using the Triangular

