#### 2.5 Randomization

This is a randomized trial and subjects are randomized into Sham Control Arm or Latera Implant Treatment Arm, after anesthetic is delivered. Treatment assignment will remain blinded to the study subject through the 3-month assessment.

The graphic below illustrates the flow of subjects in the study and potential points of study exit relative to the analysis plan (**Figure 1**, below). Subjects are enrolled at the time of consent, and the ITT population is comprised of all consented subjects. Subjects are randomized after the anesthetic is administered. Subjects in the active treatment group receive the Latera implant, while those in the Sham Control group will undergo insertion of the cannula into the nasal lateral wall, but the Latera will not be implanted. The mITT population includes all subjects who were randomized, irrespective of whether they received the study device. The PP population includes those subjects who received the study device or the Sham Control and who are followed through 3 months.

<sup>1 Kittelson JM, Emerson SS. A unifying family of group sequential test designs. Biometrics. 1999 Sep;55(3):874-82.

ST 800-A

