#### **3 ENDPOINT DEFINITIONS**

#### 3.1 Primary Endpoint

The primary endpoint of the study is the Responder Rate, assessed 3 months post-procedure in the per protocol population of the Latera and Sham arms. Responder Rate is defined as the proportion of subjects with at least one (1) NOSE class improvement or at least 20% NOSE score reduction.

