### STATISTICAL ANALYSIS PLAN

The following populations will be analyzed in the study:

**Intention-to-Treat (ITT) Population:** The ITT analysis will be performed on all enrolled subjects in the study, irrespective of adherence with the entry criteria, treatment actually received, subsequent withdrawal, or deviation from the Clinical Investigational Plan. Subjects who are enrolled but not randomized will not be included in the analytic datasets.

Modified Intention-to-Treat (mITT) Population: The mITT Population will comprise of ITT subjects who received anesthetic, regardless of whether they received the Latera Implant or underwent the Sham procedure. Subjects who are in the mITT population assigned to the Latera Implant Arm but who do not receive the device are followed for 3 months for safety-related endpoints and will be exited after 3-month follow-up assessments.

**Per Protocol Population:** The PP analysis will be performed on randomized subjects a) in the Sham Control Arm, and b) in the Latera Implant Arm who were treated and who had NOSE score assessments within the 3-month follow-up clinic visit window. The primary endpoint will be evaluated on this population. Subjects will be analyzed according to the procedure actually received in the event of mis-randomization. Unblinded subjects in either arm prior to the 3-month time point are not included in the PP analysis.

The point of enrollment into the study occurs when the subject signs the Informed Consent Form (ICF) and meets all eligibility criteria.

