#### 5.4.4 Interim Analyses

There will be two planned interim analyses and one final analysis for this study (**Table 1**, below). The stopping boundaries are derived using the Triangular Method [see footnote 1], which is a special case of Unified Family (Power) boundaries. A shape parameter ( $\tau$ ) of 0.65 will be used, and both boundaries will be non-binding. Interim analyses will occur when approximately 22 and 60 total subjects have been enrolled with 3-month assessments. The stopping boundaries are

ST 800-A

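### The Per Protocol set that carries the primary test has two conflicting definitions, and the operative one can be read as setting its conditions on the Latera arm only

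*SAP*

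**What the plan says.** SAP 3.1 places the primary endpoint in the PP set: it is "assessed 3 months post-procedure in the per protocol population of the Latera and Sham arms". Protocol 3.2 says the same.

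That set is defined twice in each document.

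- **SAP 4.1.1 and Protocol 6.2** use a list with two lettered items: "randomized subjects a) in the Sham Control Arm, and b) in the Latera Implant Arm who were treated". Item a) names the sham arm and stops. Item b), given in full, is "in the Latera Implant Arm who were treated and who had NOSE score assessments within the 3-month follow-up clinic visit window". Both sections add that subjects are analysed by the procedure they actually received if mis-randomised.
- **SAP 2.5 and Protocol 4.3**, which introduce the flow chart, say: "The PP population includes those subjects who received the study device or the Sham Control and who are followed through 3 months". This covers both arms but mentions no visit window.

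Subjects unblinded before 3 months are excluded from the PP set in either arm (SAP 4.1.1 and 4.2, Protocol 6.3). The 3-month window is 90 ± 14 days (Protocol Table 2), that is, days 76 to 104.

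No section says how a PP subject without a 3-month NOSE is scored. SAP 5.1 bases summaries on available data. SAP 5.5 confines multiple imputation of the primary endpoint to the ITT and mITT populations.

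**The concern.** Even a per-protocol comparison needs one admission rule for both arms. If treatment and an in-window NOSE are required of Latera subjects but not of sham subjects, the arms are filtered differently after randomisation. The primary contrast then partly reflects the filter.

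The two definitions also disagree on the window, so two competent programmers could build different primary sets from the same data. This set carries the trial's only confirmatory test, and the evaluable counts that time the interim looks need the same rule. At the first look, 22 evaluable subjects are about 22/2 = 11 per arm, so one subject moves an arm's response rate by about 1/11 = 9 points.

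**Working it through.** **1. The definitions side by side**

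| Subject | SAP 4.1.1 / Protocol 6.2, conditions on b) only | Same text, conditions on both arms | SAP 2.5 / Protocol 4.3 |
|---|---|---|---|
| Sham, lost at day 40 | In, no outcome | Out | Out |
| Latera, lost at day 40 | Out | Out | Out |
| Sham, NOSE at day 115 | In | Out | Arguably in |
| Latera, NOSE at day 115 | Out | Out | Arguably in |
| Sham, cannula step not done | In | Out | Out |

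The day-115 rows differ across all three columns, so neither reading of SAP 4.1.1 removes the conflict with SAP 2.5.

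**2. The plan's own figure**

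SAP 2.4 takes 40% for sham and 70% for Latera, and concludes: "a maximum sample size of 124 evaluable subjects is required for 90% power and preserving a 2.5% (one-sided) type I error rate". Allocation is 1:1, so 124/2 = 62 per arm. SAP 5.4.4 sets looks at 22, 60 and 124 with efficacy p-value bounds 0.0005, 0.0090 and 0.0194. With unpooled variance the final drift is 0.30/√[(0.4×0.6 + 0.7×0.3)/62] = 3.52. Simulating this design gives cumulative Type I error of 0.0005, 0.0093 and 0.0251 without futility stopping, and power of 0.90. The 124 reproduces and is not affected by this point.

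**3. What a one-arm rule could do**

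Method: exact enumeration of two binomials for a single test at the final bound of 0.0194, with both arms truly at 40%. SAP 5.2 names a one-sided binomial test without a formula, so two statistics are shown: the pooled z, and the continuity-corrected z′ that SAP 5.4.4 gives for the interims. With 62 v 62 under a symmetric rule, rejection is 0.0186 (pooled) and 0.0136 (z′).

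*Case A: sham subjects without a NOSE stay in the denominator as non-responders (assumption).* Ten per cent dropout on 62/0.9 = 69 randomised leaves 7 without an outcome. The sham rate reads 0.40×62/69 = 24.8/69 = 35.9%.

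*Case B: missing values are dropped, and the window is enforced only in Latera.* Assume 10% attend out of window with response 20 points lower. If r is the in-window rate, 0.9r + 0.1(r − 0.20) = 0.40, so r = 0.42. About 0.9×62 = 56 Latera subjects at 42% are compared with 62 sham subjects at 40%. With response 20 points higher, r = 0.38.

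| Scenario | Pooled z | z′ |
|---|---|---|
| Symmetric, 62 v 62 | 0.019 | 0.014 |
| A: 7 sham kept as non-responders | 0.059 | 0.041 |
| A: 3 sham kept as non-responders | 0.028 | 0.023 |
| No-bias reference for B, 56 v 62 | 0.020 | 0.013 |
| B: late attenders 20 points lower | 0.033 | 0.022 |
| B: late attenders 20 points higher | 0.0115 | 0.007 |

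Case B needs its own reference because exact rejection rates shift with arm size. With 5% out of window and response 20 points lower, the pooled figure is 0.030, against a no-bias 0.023 at 59 v 62.

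If the 7 sham subjects in case A were scored as responders instead, the sham rate would read (24.8 + 7)/69 = 46.1%, a tilt against Latera. If they are simply not counted, the missing values cause no change from the symmetric rule.

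**The case against.** A reader might infer that the rule as written tilts the primary comparison toward Latera. The documents do not support that.

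- The closing clauses can grammatically attach to both lettered items. Several places favour this: the two-arm definition in SAP 2.5 and Protocol 4.3, the responder definition in SAP 5.2 (which needs a 3-month NOSE), the interim counts in SAP 5.4.4 (subjects with 3-month assessments, whatever the arm), and the early-unblinding exclusion for both arms.
- No section scores a sham subject without a NOSE as a non-responder. Under the available-data sentence in SAP 5.1, such subjects drop out of numerator and denominator, and case A disappears.
- The direction of case B is assumed. The documents give neither an out-of-window rate nor the response of late attenders, and the opposite assumption reverses the effect. Under z′ the adverse 10% case is 0.022, close to the nominal 0.0194.

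All of this stands against a claim of known bias. It does not rescue the definition. Where the authors mean both arms in the unblinding rule they say so, and the lettered list does not. Available-data handling does not reach case B either, because an out-of-window NOSE is present, not missing. Even on the two-arm reading, the window conflict with SAP 2.5 remains.

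**Conclusion.** The defect is one of definition. The set for the only confirmatory test has two rules that do not match, and the operative one can be read as conditioning the Latera arm alone. That should be corrected.

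A bias in a known direction is not established. The Type I figures are conditional illustrations for a single test at the final bound with a common 40% rate. The rise to 0.059 (pooled) or 0.041 (z′) requires a non-responder scoring rule that the plan does not contain. The one-arm window moves the pooled figure from 0.020 to 0.033 or 0.0115, and z′ from 0.013 to 0.022 or 0.007, depending on an assumed 10% out-of-window rate and an assumed 20-point difference in response.

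**What to change.** Use one definition in SAP 4.1.1, SAP 2.5, Protocol 6.2 and Protocol 4.3, and for the evaluable counts at the interims:

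> The PP population comprises randomised subjects in either arm who received the Latera Implant or the Sham procedure, had a NOSE assessment within the 3-month visit window (90 ± 14 days), and were not unblinded before that assessment.

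The existing sentence on analysis by procedure received can stay. Every PP subject then has an in-window NOSE, so no scoring rule for missing values is needed in this set.

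The cost is a short text change in each document, best made before the first interim. It needs no new data or subjects. The downside is that the evaluable sham count may fall by the few subjects without an in-window NOSE.

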5.4. Retrievals and Re-Implantation

There is a low incidence of where the Latera Implant is removed, post-implant nasal manipulation by a patient. If this occurs, the Latera Implant may be re-implanted, within 30 days, of the removal at the discretion of the investigator, continuing the follow up schedule from the Index Procedure. An addendum to the Informed Consent is required to be reviewed and signed by subject. See Section 6.2 for analysis implications.

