#### 2.7 Retrievals and Re-Implantation

There is a low incidence of where the Latera Implant is removed, post-implant nasal manipulation by a patient. If this occurs, the Latera Implant may be re-implanted, within 30 days, of the removal at the discretion of the investigator, continuing the follow up schedule from the Index Procedure. An addendum to the Informed Consent is required to be reviewed and signed by subject. See Section 4.1.1 for analysis implications.

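### The deciding superiority test is run on a per-protocol set fixed by post-randomisation events; all randomised subjects, analysed as randomised, should be primary

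*SAP*

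**What the plan says.** **Population for the test.** SAP 3.1 and Protocol 3.2 define the primary endpoint as the responder rate "assessed 3 months post-procedure in the per protocol population of the Latera and Sham arms". SAP 4.1.1 repeats it: "The primary endpoint will be evaluated on this population". The test is one-sided for superiority (SAP 5.2).

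**Who is in the set.** SAP 4.1.1 and Protocol 6.2 take randomised subjects in the Sham arm, and those "in the Latera Implant Arm who were treated and who had NOSE score assessments within the 3-month follow-up clinic visit window". SAP 4.1.1 adds: "Unblinded subjects in either arm prior to the 3-month time point are not included in the PP analysis" (also SAP 4.2, Protocol 6.3). Both documents analyse mis-randomised subjects by the procedure they received. SAP 2.5 and Protocol 4.3 word the set differently: "The PP population includes those subjects who received the study device or the Sham Control and who are followed through 3 months".

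**Timing.** Randomisation follows the anaesthetic and precedes the implant or sham step (SAP 2.5, Protocol 5.2).

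**Other populations.** ITT is all consented subjects in SAP 2.5, but SAP 4.1.1 leaves non-randomised subjects out of the datasets. mITT is all randomised subjects in 2.5 and those given anaesthetic in 4.1.1. Latera subjects who do not get the device "are followed for 3 months for safety-related endpoints and will be exited after 3-month follow-up assessments" (SAP 4.1.1), whereas Protocol Table 2 lists NOSE at Visit 5 without exception.

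**Retrievals.** SAP 2.7 says "See Section 4.1.1 for analysis implications" and Protocol 5.4 says "See Section 6.2 for analysis implications". Neither target section mentions retrieval or re-implantation.

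**Sensitivity analyses.** SAP 5.5 plans multiple imputation and a tipping-point analysis of the primary endpoint in ITT and mITT, as secondary analyses. The imputation model lists 13 baseline covariates and not treatment arm.

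**The concern.** In a superiority trial the case for causal attribution rests on comparing the groups that randomisation formed. Being treated, returning inside the window and staying blinded all happen after assignment and may relate to both arm and outcome. If those dropped from Latera respond less often than those kept, and Sham loses no comparable subjects, the Latera rate rises without any device effect. The reverse pattern would hide an effect.

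The secondary analyses do not remove the problem. No rule says what follows if they disagree with the per-protocol result, and an imputation model without arm tends to pull imputed outcomes in the two arms together.

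The membership rules also leave room for choice. The conditions in SAP 4.1.1 can be read as applying to Latera only or to both arms, and the status of retrieved subjects is open. Two statisticians could build different primary datasets from the same text.

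**Working it through.** **1. The plan's own figure.** Inputs (SAP 2.4, 5.4.4): 40% v 70%, one-sided 0.025, 90% power, looks at 22/60/124, triangular boundary with tau 0.65, non-binding.
- Fixed design, unpooled variance: (1.960 + 1.2816)² × (0.4×0.6 + 0.7×0.3) / 0.30² = 10.507 × 0.45/0.09 = 52.5 per arm, 105.1 in total. The three-look design raises this to 123.2, hence 124, with power 0.901.
- Boundary: Z = C(0.65√t + 1/√t), with t = 22/124, 60/124 and 1. Setting overall alpha to 0.025 with futility ignored gives one-sided p = 0.0005/0.0090/0.0194. The plan's efficacy bounds reproduce.

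**2. Type I error under selective exclusion.** Exact three-look binomial enumeration at 11/30/62 per arm, futility not enforced. The interims use the SAP 5.4.4 continuity-corrected statistic, signed. SAP 5.2 gives no formula for the final test, so a pooled z is assumed there. With true response 40% in both arms, a share x of an arm excluded and response rate r among those excluded, the retained rate is (0.40 − x·r)/(1 − x).

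| Latera excluded | Their response | Sham excluded (all non-responders) | Retained rates, Latera v Sham | Type I error |
|---|---|---|---|---|
| 0 | – | 0 | 40.0% v 40.0% | 2.3% |
| 10% | 40% | 0 | 40.0% v 40.0% | 2.3% |
| 10% | 20% | 0 | 42.2% v 40.0% | 4.0% |
| 10% | 0% | 0 | 44.4% v 40.0% | 6.5% |
| 10% | 0% | 5% | 44.4% v 42.1% | 4.1% |
| 10% | 0% | 10% | 44.4% v 44.4% | 2.4% |

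For example, (0.40 − 0)/(1 − 0.10) = 0.444. The shares and response rates are assumptions; the documents give no rate for the stated exclusions.

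**3. Boundary if the final count changes.** At 124 randomised, 0.0194 stands. At 150, leaving all three bounds as they are gives overall alpha 0.0257. Re-deriving from the same triangular formula at 22/60/150 gives efficacy 0.0002/0.0068/0.0205 and interim futility 0.874/0.319. Keeping 0.0005 and 0.0090 instead requires a final bound of about 0.0186, which leaves the triangular family.

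**4. Power.** Same enumeration, futility enforced (not enforced in brackets). The ceiling is 150/2 = 75 per arm: the 150 are counted at consent and eligibility, and subjects not treated within 30 days exit before randomisation (Protocol 5.1).
- Current per-protocol plan, 62 per arm, 70% v 40%: 86% (91%).
- All randomised, 75 per arm, re-derived bounds, 70% v 40%: 93% (96%).
- The same, if 70% describes per-protocol subjects and 10% of Latera subjects become failures, 0.9 × 70% = 63% v 40%: 75% (79%).

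The 75-per-arm figures are before any loss of information from imputed scores.

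**The case against.** The strongest reply is that the all-randomised analysis already exists. SAP 5.5 prespecifies ITT and mITT analyses with imputation and a tipping-point analysis that covers every possible imputed outcome, so the dispute is over rank. That is right. But rank decides which result declares success, and the planned imputation needs arm added before it can carry that role.

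A second reply is that the exclusions may be balanced. SAP 2.5 and Protocol 4.3 require receipt of the assigned procedure and follow-up in both arms, and early unblinding removes subjects from either arm. With equal exclusion of non-responders the illustration shows almost no inflation. This stands as a limit on size. It does not show that exclusions will be balanced, and nothing in the plan ensures it.

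A third reply is that several items here are drafting matters. The broken retrieval references and the differing ITT and mITT wording are. They are included because a change of primary population cannot be made cleanly without settling them.

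**Conclusion.** The concern holds: the confirmatory comparison is not protected by randomisation, and the plan already has most of what is needed to protect it. It should be fixed. The direction and size of any bias cannot be settled from the documents.

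Four stronger readings may tempt a reader and are not supported.
- **That only the Latera arm is filtered.** SAP 4.1.1 can be read so, but SAP 2.5 and Protocol 4.3 condition both arms. This is an ambiguity to resolve.
- **That retrieved subjects leave the per-protocol set.** The 10% retrieval allowance in SAP 2.4 hints at it, but no text says so. Read literally, a retrieved subject with an in-window NOSE stays in.
- **That the trial's type I error is 6.5%.** That figure needs 10% one-sided exclusion, made up entirely of non-responders. It is the extreme of an assumed range whose lower end is 2.3%.
- **That the boundary must be restated in any case.** It need be only if the final look moves from 124, and even at 150 the uncorrected alpha is 0.0257.

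**What to change.** 1. Make all randomised subjects, analysed as randomised, the primary population in SAP 3.1/4.1.1 and Protocol 3.2/6.2. Restrict the rule on analysis by procedure received to the supportive per-protocol analysis. Keep unimplanted, retrieved, re-implanted and early-unblinded subjects in their assigned arm, with their observed Visit 5 NOSE taken before crossover.
2. State that Visit 5 NOSE is collected from every randomised subject, and align the safety-only wording for unimplanted Latera subjects in 4.1.1 with the schedule.
3. For missing scores, use the planned multiple imputation with treatment arm added and a named reduced model at the interims, where 13 covariates may not be estimable at 22 subjects. Keep the tipping-point analysis.
4. Keep per-protocol as supportive, with the same conditions in both arms and an explicit line on retrieved and re-implanted subjects. Reconcile ITT, mITT and per-protocol wording across SAP 2.5/4.1.1 and Protocol 4.3/6.2.
5. Name the final number of randomised subjects. If it is not 124, re-derive all efficacy and futility bounds from the triangular tau 0.65 design, or say openly that the interim efficacy bounds are kept and give the adjusted final bound.
6. Say which population the 70% describes, and restate power.

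The cost is protocol and SAP text, one added model term, and possibly a new boundary table and a lower stated power. The Visit 5 NOSE is already scheduled, and Protocol 4.4 already follows subjects who withdraw after anaesthesia through 3 months. No extra enrolment is proposed.
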